7.1.1.2 Week 2 (\pm 7 Days)–Phone Visit for SOC-alone Subjects

- Review AEs/SAEs
- Review concomitant medications

7.1.1.3 Week 4 (\pm 7 Days)–If Subject with no Previous Experience of Self-injection is Randomized to AMG 145+ SOC

- Vital signs: sitting blood pressure (BP), heart rate (HR)
- Review AEs/SAEs
- Review concomitant medications
- Train subject on self-injection of AMG 145
- Observe subject self- inject AMG 145 at study site (AMG 145 administration must occur after other procedures). Dispense IP quantity for at-home injections for subjects on Q2W dosing only

7.1.1.4 Week 4 (\pm 7 Days) – Phone Visit for SOC-alone Subjects

- Review AEs/SAEs
- Review concomitant medications

7.1.1.5 Week 8 (\pm 7 Days)–If Subject with no Previous Experience of Self-injection is Randomized to AMG 145 + SOC and Selects QM Regimen

- Vital signs: sitting blood pressure (BP), heart rate (HR)
- Review AEs/SAEs
- Review concomitant medications
- Train subject on self-injection of AMG 145
- Observe subject self- inject AMG 145 at study site (AMG 145 administration must occur after other procedures)

7.1.1.6 Week 8 (\pm 7 Days)–Phone Visit for SOC-alone Subjects

- Review AEs/SAEs
- Review concomitant medications

7.1.1.7 Week 12 (\pm 7 Days)

- Vital signs: sitting blood pressure (BP), heart rate (HR)
- Review AEs/SAEs
- Review concomitant medications
- Blood draw for fasting lipids (\geq 9 hour fasting sample), ApoA1, ApoB, Lp(a), Vitamin E (sample drawn, testing by reflex when LDL-C is $<$ 25 mg/dL), and chemistry, hematology, HbA1c, Anti-AMG 145 antibodies
- HCV viral load (in subjects positive for HCV)
- Urine pregnancy
- Urinalysis
- Urine microalbumin
- Dispense IP quantity for at-home injections for subjects on AMG 145 + SOC
- IP reconciliation

7.1.1.8 Week 24 Visit (\pm 7 Days)

- Vital signs: sitting blood pressure (BP), heart rate (HR)
- Review AEs/SAEs
- Review concomitant medications
- Blood draw for fasting lipids (\geq 9 hour fasting sample), ApoA1, ApoB, Lp(a), Vitamin E (sample drawn, testing by reflex when LDL-C is $<$ 25 mg/dL), chemistry, hematology, HbA1c, Anti-AMG 145 antibodies
- HCV viral load (in subjects positive for HCV)
- Urine pregnancy
- Urinalysis
- Dispense IP quantity for at-home injections for subjects on AMG 145 + SOC
- IP reconciliation

7.1.1.9 Week 36 Visit (\pm 7 Days)

- Vital signs: sitting blood pressure (BP), heart rate (HR)
- Review AEs/SAEs
- Review concomitant medications
- Dispense IP quantity for at-home injections for subjects on AMG 145 + SOC
- IP reconciliation

7.1.1.10 Week 44 (\pm 7 days)–for Subjects on QM Regimen Only

- Vital signs: sitting blood pressure (BP), heart rate (HR)
- Review AEs/SAEs
- Review concomitant medications
- In-office IP administration (either self-injection or HCP administered)
- IP reconciliation

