6.1.1 Dosage, Administration, and Schedule

IP will be administered SC in accordance with instructions in the IPIM.

IP administration at each on-site visit must be done after vital signs and blood draw procedures, as applicable. The date, time, and amount (as designated by partial or full injection of AMG 145) will be recorded on the individual subject's worksheet and/or electronic Case Report Form (eCRF). After IP administration on Day 1 or Week 48 for subjects initially randomized to standard of care (SOC)-alone, subjects should be kept for observation for at least 30 minutes before being discharged.

On Day 1 of the study, subjects randomized to AMG 145 plus SOC will be trained on self-administration of study drug and will self-administer IP at the investigational site,

under the supervision of a healthcare provider. Subjects without prior experience of self-injection of AMG 145 will subsequently visit the site to self-administer AMG 145 at Week 2 (Q2W regimen only), Week 4 (Q2W and QM regimens) and Week 8 (QM regimen only). After the Week 4 visit for subjects on Q2W regimen or Week 8 visit for subjects on QM regimen, IP can be administered at a location external to the study site, using the prefilled AI/Pen or Personal Injector provided. Thereafter, AMG 145 will be self-administered or administered by a caregiver at home.

The subject (or designee) must have demonstrated competency in administration of SC injections before self-injection will be permitted. For subjects that prefer not to self-administer IP, IP may be administered at the site.

Subjects will receive training on IP use prior to home administration; however IP may be administered at the site if subjects prefer not to self-inject AMG 145.

Subjects randomized to AMG 145 + SOC and selecting Q2W IP administration will receive a total volume of 1.0 mL via 1 prefilled AI/pen injection every 2 weeks.

Subjects randomized to AMG 145 + SOC and selecting QM IP administration will receive a total volume of 3.0 mL monthly via 3 separate prefilled AI/pen injections or a total volume of 3.5 mL via a single Personal Injector. Injection sites should be rotated throughout the study. For the AI/pen, the SC injections should be administered in a consecutive fashion with all injections completed within 30 minutes.

The dosing schedule is also described by a [schema](#) in the protocol synopsis.

For further details regarding IP administration procedures, the IPIM should be consulted.

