7.1.1.20 Week 72 (\pm 7 Days)

- Vital signs: sitting blood pressure (BP), heart rate (HR)
- Review AEs/SAEs
- Review concomitant medications
- Dispense IP quantity for at-home injections
- IP reconciliation

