10.1.2 Secondary Endpoints

- Percent change from baseline in LDL-C at Week 48 and Week 104
- Change from baseline in LDL-C at Week 48 and Week 104

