10.4.2.3 Exploratory Endpoint Analyses

The percent change and change from baseline in laboratory based exploratory endpoints at each scheduled visit will be summarized. For achieving LDL-C < 70 mg/dL, subjects missing LDL-C for a particular planned visit will be considered as not achieving LDL-C < 70 mg/dL. For continuous exploratory endpoints, the same model as for the secondary endpoint analyses may be used for estimating treatment group means and differences at weeks 48 and 104.

Subgroup analyses for exploratory endpoints may be conducted on baseline covariates specified in Section 10.1.6.

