8.4.7 Exposure to Investigational Product

Descriptive statistics will be produced to describe the patient-month exposure to investigational product, by treatment group for both the ICOAS and IAAS sets as well as overall. Exposure definitions are provided in [Section 5.3](#).

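### LDL-C at Weeks 48 and 104 is drawn one dosing interval after a scheduled in-office dose, so it can overstate efficacy under home use and is not like for like with other visits

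*Protocol*

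**What the plan says.** **Dosing.** After training, home dosing is the default (Protocol 6.1.1): "Thereafter, AMG 145 will be self-administered or administered by a caregiver at home". Site dosing remains open by preference: "For subjects that prefer not to self-administer IP, IP may be administered at the site".

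**Endpoint visits.** Protocol 10.1.2 names "Percent change from baseline in LDL-C at Week 48 and Week 104", and absolute change at the same two visits. Shortly before each, the schedule lists "In-office IP administration (either self-injection or HCP administered": Week 44 (7.1.1.10) and Week 100 (7.1.1.23) for QM, Week 46 (7.1.1.12) and Week 102 (7.1.1.24) for Q2W. Appendix A marks these doses for subjects with and without in-home experience. SOC-alone subjects have only phone contacts at Weeks 44 and 46 (7.1.1.11, 7.1.1.13).

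**Other lipid visits.** At Week 24 the only product step apart from reconciliation is "Dispense IP quantity for at-home injections for subjects on AMG 145 + SOC" (7.1.1.8). Week 72, the last visit before the Week 84 draw, has "Dispense IP quantity for at-home injections" (7.1.1.20). Weeks 116, 128 and 140, before the Week 152 draw, are the same (7.1.1.26).

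**Analysis.** Protocol 10.4.2.2 specifies a mixed model with visit and treatment-by-visit terms, and says group differences will be estimated for secondary and exploratory endpoints. Protocol 10.4.2.3 then says that this model may be used for "estimating treatment group means and differences at weeks 48 and 104". LDL-C at every scheduled visit is an exploratory endpoint (10.1.3), and the interim SAP summarises it descriptively at each lipid visit (3.2, 8.4.2). On exposure, SAP 8.4.7 says "Descriptive statistics will be produced to describe the patient-month exposure to investigational product". The formula in SAP 5.3 runs from first dose to EOIP + 28 days, capped at EOS or data cutoff.

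**The concern.** The secondary objective is long-term efficacy, and long-term use here means home use. A subject who skips home doses but attends for the clinic dose reaches Week 48 or 104 with the latest dose secured. SOC-alone subjects receive no such dose, so the Week 48 between-group difference moves in the same direction as the AMG 145 mean.

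The second risk is to statements about persistence. After Week 48 all subjects receive AMG 145, so durability has to be read across visits. For most subjects the main lipid series (Weeks 24, 48, 84, 104, 152) alternates between draws after home dosing and draws after a clinic dose. Part of any rise or fall between neighbouring visits could reflect visit type alone.

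The planned exposure summary would not reveal the problem. It does not subtract missed doses, and neither document plans a table from the IP reconciliation done at most visits.

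**Working it through.** The plan states no adherence or carry-over figure, so there is no figure of its own to reproduce. Its one precision statement (Protocol 10.2) concerns adverse-event incidence and does not bear on this point.

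**Step 1. Count the doses not scheduled as in-office between the last in-office dose and each lipid draw** (Protocol 7.1.1 and Appendix A; Q2W every 2 weeks, QM every 4).

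| Draw | Q2W | QM |
|---|---|---|
| Week 24, no self-injection experience (last in-office dose Week 4 / Week 8) | 9 | 3 |
| Week 24, experienced (Day 1) | 11 | 5 |
| Week 48 (Week 46 / Week 44) | 0 | 0 |
| Week 84, randomized to AMG 145 (Week 46 / Week 44) | 18 | 9 |
| Week 84, SOC-alone crossover without experience (Week 52 / Week 56) | 15 | 6 |
| Week 104 (Week 102 / Week 100) | 0 | 0 |
| Week 152 (Week 102 / Week 100) | 24 | 12 |

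There are two exceptions to the alternation. Week 12 follows an in-office dose for inexperienced QM subjects (Week 8). The Week 60 draw, taken only in subjects on placebo or SOC in the parent study and then SOC-alone, follows an observed Week 56 dose for inexperienced QM crossovers.

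**Step 2. Size, under an illustrative linear model.** Let m be the share of home doses missed, q the share of one dose's contribution left after one further interval, and E the full effect. A dose k intervals before the latest one then has weight (1 − q)qᵏ.

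- Last dose at home: expected effect = (1 − m)E.
- Last dose in office: expected effect = [(1 − q) + q(1 − m)]E = (1 − mq)E.
- Overstatement = (1 − mq)E − (1 − m)E = m(1 − q)E; ratio = (1 − mq)/(1 − m).

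A simulation at m = 0.2, q = 0.25 gave retained effects of 0.801 and 0.950, against 0.80 and 0.95 from the formulas.

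With E assumed at 50 to 60 percentage points of LDL-C change (not in the documents), the overstatement in points, with the ratio in brackets, is:

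| m | q = 0 | q = 0.25 | q = 0.5 |
|---|---|---|---|
| 5% | 2.5–3.0 (1.05) | 1.88–2.25 (1.04) | 1.25–1.5 (1.03) |
| 10% | 5–6 (1.11) | 3.75–4.5 (1.08) | 2.5–3.0 (1.06) |
| 20% | 10–12 (1.25) | 7.5–9.0 (1.19) | 5–6 (1.13) |
| 30% | 15–18 (1.43) | 11.25–13.5 (1.32) | 7.5–9.0 (1.21) |

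The q = 0 column is the upper bound: one dose restores the whole effect and earlier misses leave no trace.

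**Step 3. Can the SAP windows show the contrast?** SAP Appendix A puts a scheduled draw at day 7 × week + 1. Week 84 is day 589, inside the Week 96 lipid window (588, 700]. Week 152 is day 1065, inside the Week 104 window (> 700). The closest-record rule would normally keep the Week 104 draw (day 729), but where that is missing the Week 152 draw would stand in for it. As written, the windows mix the two visit types.

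**The case against.** The strongest case against the point is this. The study is descriptive and its primary objective is safety. Measuring LDL-C after an assured dose is a defensible way to characterise efficacy. LDL-C at every lipid visit is already summarised by group, so Week 24 results will be seen. Protocol 10.4.2.2 can be read as promising differences for exploratory endpoints too, which include LDL-C at every visit. The SAP provided is an interim one written to Amendment 2, so its silence on missed doses does not settle what a final SAP contains. Nor would visit labels isolate adherence: regimens may be switched after Week 12, background therapy may change after unblinding, and visit type is mixed with time.

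Much of this stands. It limits the point to interpretation of a secondary endpoint and makes the remedy cheap. It does not remove the point: 10.4.2.3 names model-based estimates only at Weeks 48 and 104, and neither document mentions or contrasts visit type.

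A reader might also infer that the Week 48 and 104 draws cannot show any loss from missed doses. The documents do not support that:

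- Only the latest dose is secured, and earlier misses still show in proportion q.
- Subjects who stop IP are asked to continue observations (Protocol 8.1), and controlled-period analyses use the full analysis set (10.1.5), so loss from stopping can appear at Week 48. It is less certain at Week 104, where 10.1.5 allows restriction to subjects receiving IP.
- In-office visits can be missed, and the ±7-day windows on both visits let the gap vary by up to 14 days either way.
- Subjects who choose site dosing dilute the contrast.

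**Conclusion.** The point holds as one of interpretation and reporting. The schedule contrast is certain: by schedule, no home doses fall between the last in-office dose and the Week 48 and 104 draws, against 3 to 24 at Weeks 24, 84 and 152. The direction follows for any m > 0 and q < 1: the endpoint draws can overstate efficacy under home use.

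The size is not known. Over m = 5% to 30% and q = 0 to 0.5, the overstatement is a factor of 1.03 to 1.43. This rests on assumed m and q, a linear dose contribution, and attendance at the in-office visit. A reader might take m × 50–60 points as the expected bias. It is only a ceiling, and the 50 to 60 points are themselves an assumption.

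The documents give no reason for the in-office doses, and nothing about their purpose should be inferred. The primary safety endpoint is not affected.

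**What to change.** Leave dosing and visits as they are, and change the reporting.

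1. **Protocol 10.4.2.2 and 10.4.2.3.** Use the planned mixed model to report the AMG 145 + SOC minus SOC-alone LDL-C difference with 95% CI at Week 24 beside Week 48, and AMG 145 means at Weeks 84 and 152 beside Week 104. In the controlled period, Week 24 is the between-group comparison furthest from in-office dosing.
2. **Same sections.** State that the Week 48 and 104 estimates follow a scheduled in-office last dose. Base any statement on persistence on visits of the same type (Weeks 48 and 104 together; Weeks 24, 84 and 152 together), noting that regimen and background therapy may also have changed.
3. **SAP Appendix A.** Add Week 84 and Week 152 lipid windows, so that these draws no longer fall into Weeks 96 and 104.
4. **SAP 8.4.7.** Add doses taken over doses expected, from the IP reconciliation and dosing records. Protocol 6.1.1 allows dosing details to sit on a worksheet rather than the eCRF, so this can go only as far as the data were captured.

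The cost is a few more rows from a model already planned, a window update, one adherence table, and a reported long-term effect that may look slightly smaller.

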7.1.1.11 Week 44 (\pm 7 Days)–Phone Visit for SOC-alone Subjects

- Review AEs/SAEs
- Review concomitant medications

7.1.1.12 Week 46 (\pm 7 days)–for Subjects on Q2W Regimen Only

- Vital signs: sitting blood pressure (BP), heart rate (HR)
- Review AEs/SAEs
- Review concomitant medications
- In-office IP administration (either self-injection or HCP administered)
- IP reconciliation

7.1.1.13 Week 46 (\pm 7 Days)–Phone Visit for SOC-alone Subjects

- Review AEs/SAEs
- Review concomitant medications

7.1.1.14 Week 48 Visit (\pm 7 Days)

- Vital signs: sitting blood pressure (BP), heart rate (HR)
- Review AEs/SAEs
- Review concomitant medications
- Body weight
- Blood draw for fasting lipids (\geq 9 hour fasting sample), ApoA1, ApoB, Lp(a), Vitamin E (sample drawn, testing by reflex when LDL-C is $<$ 25 mg/dL), hsCRP, chemistry, hematology, HbA1c, Anti-AMG 145 antibodies, coagulation
- HCV viral load (in subjects positive for HCV)
- Urine pregnancy
- Urinalysis

- Urine microalbumin
- Train subject on self-injection of AMG 145 (for subjects randomized to SOC-alone in Year 1)
- Observe subject self- inject AMG 145 at study site for subjects randomized to SOC-alone in Year 1 (AMG 145 administration must occur after other procedures).
- Dispense IP quantity for at-home injections to subjects with previous experience of self-injection with AMG 145

7.1.1.15 Week 50 (\pm 7 Days)–Additional Procedures for Subjects Randomized to SOC–alone in Year 1 with no Previous Experience of Self-injection and Selects Q2W Regimen

- Vital signs: sitting blood pressure (BP), heart rate (HR)
- Review AEs/SAEs
- Review concomitant medications
- Train subject on self-injection of AMG 145
- Observe subject self- inject AMG 145 at study site (AMG 145 administration must occur after other procedures)

7.1.1.16 Week 52 (\pm 7 Days)–Additional Procedures for Subjects Randomized to SOC–alone in Year 1 with no Previous Experience of Self-injection

- Vital signs: sitting blood pressure (BP), heart rate (HR)
- Review AEs/SAEs
- Review concomitant medications
- Train subject on self-injection of AMG 145
- Observe subject self- inject AMG 145 at study site (AMG 145 administration must occur after other procedures)
- Dispense IP quantity for at-home injections for subjects on Q2W dosing only

7.1.1.17 Week 56 (\pm 7 Days)–Additional Procedures for Subjects Randomized to SOC–alone in Year 1 with no Previous Experience of Self-injection and Selects QM Regimen

- Vital signs: sitting blood pressure (BP), heart rate (HR)
- Review AEs/SAEs
- Review concomitant medications
- Train subject on self-injection of AMG 145
- Observe subject self- inject AMG 145 at study site (AMG 145 administration must occur after other procedures)

7.1.1.18 Week 60 (\pm 7 Days)

- Vital signs: sitting blood pressure (BP), heart rate (HR)
- Review AEs/SAEs
- Review concomitant medications

- Dispense IP quantity for at-home injections
- IP reconciliation

7.1.1.19 Week 60 (\pm 7 Days)—Additional Procedures for Subjects Randomized to Placebo or SOC in Parent Study and Randomized to SOC-alone in Year 1

- Blood draw for fasting lipids (\geq 9 hour fasting sample), ApoA1, ApoB, Lp(a), Vitamin E (sample drawn, testing by reflex when LDL-C is $<$ 25 mg/dL), chemistry, and hematology
- HCV viral load (in subjects positive for HCV)
- Urine pregnancy test
- Urinalysis
- Urine microalbumin

7.1.1.20 Week 72 (\pm 7 Days)

- Vital signs: sitting blood pressure (BP), heart rate (HR)
- Review AEs/SAEs
- Review concomitant medications
- Dispense IP quantity for at-home injections
- IP reconciliation

7.1.1.21 Week 84 (\pm 7 Days)

- Vital signs: sitting blood pressure (BP), heart rate (HR)
- Review AEs/SAEs
- Review concomitant medications
- Urine pregnancy test
- Blood draw for fasting lipids (\geq 9 hour fasting sample), ApoA1, ApoB, Lp(a), Vitamin E (sample drawn, testing by reflex when LDL-C is $<$ 25 mg/dL), chemistry, hematology, and anti-AMG 145 antibodies
- HCV viral load (in subjects positive for HCV)
- Urinalysis
- Urine Microalbumin
- Dispense IP quantity for at-home injections
- IP reconciliation

7.1.1.22 Week 96 (\pm 7 Days)

- Vital signs: sitting blood pressure (BP), heart rate (HR)
- Review AEs/SAEs
- Review concomitant medications
- Dispense IP quantity for at-home injections

- IP reconciliation

7.1.1.23 Week 100 (\pm 7 Days)–for Subjects on QM Regimen Only

- Vital signs: sitting blood pressure (BP), heart rate (HR)
- Review AEs/SAEs
- Review concomitant medications
- In-office IP administration (either self-injection or HCP administered)
- IP reconciliation

7.1.1.24 Week 102 (\pm 7 Days)–for Subjects on Q2W Regimen Only

- Vital signs: sitting blood pressure (BP), heart rate (HR)
- Review AEs/SAEs
- Review concomitant medications
- In-office IP administration (either self-injection or HCP administered)
- IP reconciliation

7.1.1.25 Week 104 (\pm 7 Days)

- Vital signs: sitting blood pressure (BP), heart rate (HR)
- Review AEs/SAEs
- Review concomitant medications
- Urine pregnancy test
- Body weight
- Physical exam
- Blood draw for fasting lipids (\geq 9 hour fasting sample), ApoA1, ApoB, Lp(a), Vitamin E (sample drawn, testing by reflex when LDL-C is $<$ 25 mg/dL), chemistry, hematology, hsCRP, anti-AMG 145 antibodies, HbA1c, coagulation
- HCV Viral load (in subjects positive for HCV)
- Urinalysis
- Urine microalbumin
- Dispense IP quantity for at-home injections

7.1.1.26 Weeks 116, 128, or 140 (\pm 7 Days)

- Vital signs: sitting blood pressure (BP), heart rate (HR)
- Review AEs/SAEs
- Review concomitant medications
- Dispense IP quantity for at-home injections
- IP reconciliation

7.1.1.27 Week 152 (\pm 7 Days)

- Vital signs: sitting blood pressure (BP), heart rate (HR)
- Physical exam
- Body weight
- Review AEs/SAEs
- Review concomitant medications
- Blood draw for fasting lipids (\geq 9 hour fasting sample), chemistry, hematology, anti-AMG 145 antibodies, HbA1c, coagulation
- Urine pregnancy test
- HCV Viral load (in subjects positive for HCV)
- IP reconciliation

7.1.1.28 End of Study–Wk156 (\pm 7 Days) – Phone visit

- Review AEs/SAEs
- Review concomitant medications

Completion of the study is defined as the last day that protocol-specified procedures are conducted for an individual subject. If a subject withdraws from the study early, all efforts should be made to complete and report the observations as thoroughly as possible up to the date of withdrawal. If possible, the procedures of Week 104 should be completed at the time of withdrawal if withdrawal occurs prior to W104.

7.1.2 Standardization of Study Procedures

7.1.2.1 Measurement of Vital Signs

Blood pressure (BP) and heart rate (HR) should be measured at each visit. BP should continue to be measured in the same arm as in the parent study unless a concomitant condition favors the use of a different arm. The appropriate size cuff should be used. The diastolic blood pressure (DBP) will be recorded as the pressure noted when sound disappears (Korotkoff Phase V). Blood pressure and heart rate measurements should be determined after the subject has been seated for at least 5 minutes. The subject's pulse should be measured for 30 seconds and the number should be multiplied by 2 to obtain heart rate.

7.1.2.2 Blood Sample Use

Any blood sample collected according to the Schedule of Assessments ([Appendix A](#)) may be analyzed for any of the tests outlined in the protocol and for any tests necessary to ensure subject safety. This includes testing to ensure analytical methods produce reliable and valid data throughout the course of the study. This may also include, but is

not limited to, investigation of unexpected results, incurred sample reanalysis, and analyses for method transfer and comparability.

Amgen may do additional testing on the remaining samples (ie, residual and back-up) to investigate and better understand primary hyperlipidemia and mixed dyslipidemia metabolic disorders, the dose response and/or prediction of response to AMG 145, characterize antibody response, and characterize aspects of the molecule (eg, metabolites). Results from this analysis will be documented and maintained, but may not be reported as part of this study.

